7.1.2 Standard of Care Study Procedures

- Standard of care imaging assessment with knee radiograph:
 - Knee radiograph obtained within 6 months of the screening will be used to assess the Kellgren-Lawrence (KL score)
 - A new knee radiograph will be obtained during or prior to visit 2 if no recent (within 6-month) radiograph of the target knee is available
 - Knee radiograph protocol: AP weightbearing, lateral, sunrise views
 - KL score will be assessed by a blinded musculoskeletal radiologist (one of co-investigators)

CONFIDENTIAL

7.2 Laboratory Procedures/Evaluations

7.2.1 Laboratory Evaluations

Baseline laboratory tests on peripheral venous blood drawn from patient during clinic visit #2 (if not available within the last 30 days prior to procedure.

- **Hematology:** Complete blood count (CBC)
- **Biochemistry:** Basic metabolic panel (BMP)
- **Coagulation profile:** INR
- **Pregnancy test:** point pregnancy test will be performed prior to procedure as standard procedure prior to fluoroscopic examination.

Baseline and follow-up laboratory tests on urine samples and peripheral venous blood drawn from patient during clinic visits (2, 5, 6, 7). Approximately 10 cc of blood will be collected from peripheral venous blood in each visit that requires collection of blood samples.

- **Inflammatory biomarkers:**
 - IL-6,
 - MMP (total activity assay),
 - IL1Ra,
 - sRAGE,
 - hsCRP,
 - VEGF,
 - S100 protein
- **Pain biomarkers**
 - Substance P
 - NGFb,
 - CCL2
- **Matrix degradation collagen biomarkers**
 - CTX-II and CTX-I.
- Type IV collagen markers (C4M, PRO-C4)*
- PRO-C6 measuring endothelium dysfunction*
- Synovial and cartilage markers (C2M, ARGS, CRPM, C1M, C3M)*

The current approved IRB protocol involves collection of blood and urine from all subjects at baseline, 1-month, 3-month, and 12-month follow up to analyze multiple serum, urine, and plasma biomarkers. We are requesting IRB modification to add an optional final visit for patients who completed 12 months follow up by August 31, 2024 after obtaining informed consent. This visit will include blood and urine collection similar to prior visits. No significant increase in risk. At the patient's request, this visit can be performed by a telemedicine visit, a phone call, or via a secure email to participant. In this case, the informed consent can be obtained via phone and the coordinator / investigator will sign in the presence of a witness. If the visit is performed via telemedicine or phone call, the research coordinator will ask the patient the questions and document the answers. If performed via email, the coordinator will send the questionnaire to patient using a secure email (sendsafe) and participants can email it back to

CONFIDENTIAL

This material is the property of the NYU School of Medicine and Langone Medical Center. Do not disclose or use except as authorized in writing by the study sponsor
Interventional Template Version: 12 February 2020

research coordinator or PI. This addition of a virtual visit will not increase the risk of participants; in contrary, it will provide the patient with the benefit of having a longer follow up with study team. If the visit is performed remotely, blood and urine samples, used for biomarkers and exploratory analysis points, will not be required.

* A portion of the collected material as part of the approved protocol, including blood, and urine, may be sent for additional biomarker analysis to outside laboratory /subcontractors. These additional biomarkers are marked with an Asterix above are: type IV collagen markers (C4M, PRO-C4); PRO-C6 measuring endothelium dysfunction; synovial and cartilage markers (C2M, ARGS, CRPM, C1M, C3M). All samples sent to outside collaborations / laboratories will be deidentified by date of collection and barcode as identifiers to protect subjects' identity. No additional samples will be collected as part of the modification. No additional risks to subjects are expected.

- Optional segment: The evaluation of the ADDITIONAL biomarkers in the outside lab will be optional for subjects. The biomarker analysis performed by IR-approved study team members at NYU will remain unchanged as part of the modification.
- Storage location: These samples (serum, plasma, and urine samples collected as part of the approved research protocol are stored and identified by barcodes and collection date only and kept in the NYU Langone Orthopedic Hospital. When samples are sent to an outside laboratory (optional part of the study), the remaining samples will be discarded after the biomarker analysis is performed and results obtained.
- Access to samples: IRB-approved study team members from NYU Langone Orthopedic Hospital have access to these samples.
- Protecting subject anonymity: Study team members who have access to the samples will received the blood / urine tubes labeled with study subject number and date of collection.
- Samples will be stored until the end of data analysis and study closure. All samples sent to outside collaborations / laboratories will be de-identified by date of collection and barcode

7.3 Study Schedule

7.3.1 Screening

Screening Visit (Visit 1, Day -30 to -2)- In rheumatology or vascular and interventional radiology clinic

- Obtain informed consent of potential subject (If the subject wishes to take more time to review the study before enrolling, he/she may complete the consent process at the beginning of the next visit)
- Provide a copy of informed consent and study brochure to subject
- Review subject's eligibility based on inclusion/exclusion criteria
- Collect demographic variables
- Obtain medical history
- Schedule study visits for eligible participants

CONFIDENTIAL

This material is the property of the NYU School of Medicine and Langone Medical Center. Do not disclose or use except as authorized in writing by the study sponsor
Interventional Template Version: 12 February 2020

Note: if subject prefers, visits 1 and 2 can be combined and procedures of these visits may be performed on the same day after screening and obtaining informed consent.

Those candidates who are disqualified from study entry will be logged into the Screening Log with a reason for no study entry. A copy of the consent will be provided to the subject and the original filed in the study files.

7.3.2 Enrollment/Baseline (Visit 2, Day -29 to -1)- In interventional radiology clinic

- Verify informed consent of potential participant (study consent)
- Verify subject's eligibility
- Targeted physical exam
- Administration of study questionnaires
- Previous / concomitant treatments
- Baseline MRI (if one is not available within the last 3 months)
- Baseline knee radiograph (if one is not available within the last 6 months)
- Peripheral venous blood draws and urine sample (baseline laboratory tests)
- Note: Subjects will be required to withhold pain medications 24 hours prior to screening and each visit for the evaluation of pain

7.3.3 Interventional visit (visit 3, Day 0)

- Within 30 days of visit 1
- Verify informed consent of participant verified by signature on written informed consent
- Geniculate artery embolization
- Record any immediate complications / adverse events detected during the procedure or observation period (if applicable)
- Subjects will be given a phone number to reach a physician 24 hours a day to report any adverse symptoms and receive medical advice

7.3.4 Follow-up Visits

7.3.4.1 Follow up visit at 1 day (Visit #4; day 1 +/-3 days)

- Subjects will be seen in clinic or contacted by phone or per the subject's preference the day following GAE (+3 days). As most complications of the procedure will be evident within this time period, this visit is to evaluate for early AE's. If AE is suspected based on change in pain scores or functionality, further assessment and management will be performed based on the nature of suspected adverse event.

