Population	40 patients, age 30-80, any gender, with grade 2,3, or 4 (in select subjects with no bone deformity) knee OA on the most recent knee radiographs obtained within 6 months of intervention

CONFIDENTIAL

Study Sites	Single center: NYU Langone Health Hospitals
Number of participants	Data from 40 patients will be required The study would accrue 50 patients to account for an attrition rate of 20%
Description of Study Agent/Procedure	Embozene™ Color-Advanced Microspheres are spherical, tightly calibrated, biocompatible, non-resorbable, hydrogel microspheres coated with an inorganic perfluorinated polymer used for embolization.
Key Procedures	Transcatheter arterial embolization of one or more genicular artery(ies) using Embozene™ Color-Advanced Microspheres
Statistical Analysis	The primary objective is to assess the clinical success rate, which will be summarized in terms of the observed proportion of patients manifesting a positive response and a two-sided exact 95% confidence interval (CI) per the Blyth-Still-Casella method (reference). The treatment will be declared a success if the data support the conclusion that at least 75% of treated patients show a positive response.

Schematic of Study Design

Prior to Enrollment

[figure not shown]
Day 0

Day 1

[figure not shown]
Day 30

Day 90

Day 360

CONFIDENTIAL

This material is the property of the NYU School of Medicine and Langone Medical Center. Do not disclose or use except as authorized in writing by the study sponsor
Interventional Template Version: 12 February 2020

Schedule of Activities

Visit #	Visit 1*	Visit2*	Visit 3	Visit 4**	Visit 5*	Visit 6*	Visit 7*	Visit 8***
Visit Description	Screening	Baseline	Intervention	1-day follow-up	1-month follow-up	3-month follow-up	12-month follow-up	>12 months
Eligibility screen	X							
Informed consent	X							
Demographics		X						
Medical history		X						
Adverse Events				X	X	X	X	X
Physical exam		X		X	X	X	X	X
Medication History		X			X	X	X	X
Pain VAS**		X			X	X	X	X
KOOS score		X			X	X	X	X
EQ-5D-5L scale		X			X	X	X	X
Previous treatments		X			X	X	X	X
Venous blood draws		X##	X##		X	X	X	X
Urine samples		X			X	X	X	X
Knee MRI		X ¹				X ³		
Knee radiograph		X ²						
Genicular artery embolization			X					

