
1- If not previously available (i.e., recent knee MRI within 3 months of screening); if MRI cannot be obtained on the same day due to subject preference and/or MRI scheduling related reasons, MRI can be performed anytime between the baseline visit and intervention visit
 
2- If not previously available (i.e., recent knee radiograph within 6 months of screening). Can be performed on a separate day based on appointment availability or subject's preference.
 
3- Post-procedural MRI can be done on a separate day of visit 6 based on appointment availability and subject's preference as long as it's performed within the timeframe of 3month +/- 10 days.
 
* Visit 1 and 2 can be combined based on subject preference. In that case, procedures listed in visit 2 will be performed after signing informed consent on the same day.
 
** Visit 4 (1-day follow-up) dates range can be +3 days (phone call, telemedicine, or in-person IR clinic visit determined by subject's preference and need for physical examination)
 
*** Visit 8. Optional visit for participants who completed 12 month follow up by August 31, 2024 (by invitation, voluntary, and after obtaining informed consent for this visit). This visit can be performed at any time interval within 18 months – 48 months
								

CONFIDENTIAL

post procedure. This visit can be performed by sending the questionnaire by a safe email and participants can email it back to research coordinator or PI OR by a phone call performed by research coordinator,
	
# 1, 3, 12-month follow-up dates range can be +/- 10 days
	
## The pre-procedural blood work can be done on the day of the procedure prior to performing the procedure based on subject's preference.
	
--	--	--	--

1 Key Roles

- **Principal Investigator (PI):** Will be one of two interventional radiologists performing the procedure. Will be responsible for study integrity, data monitoring, data collection, statistical analysis, and manuscript writing.

[name]

Clinical Assistant Professor of Radiology
Director, Vascular and Interventional Radiology Research Program
Department of Radiology, NYU Langone Health
[name]
[contact]
Email: [contact]

- **Co-PI:** Co-investigator involved in recruiting patients and conducting the clinical assessment for knee osteoarthritis

[name]

Associate Professor
Department of Internal Medicine, NYU Langone Orthopedic Center
[name]

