In a follow-up study, Okuno et al, described the safety and efficacy of transcatheter arterial embolization in 72 patients with mild to moderate radiographic knee OA [23]. Clinical outcomes were evaluated at 1, 4, and 6 months and then every 6 months for a maximum of 4 years. Mean WOMAC pain scores significantly decreased from baseline to 1, 4, 6, 12, and 24 months after treatment (12.1 vs 6.2, 4.4, 3.7, 3.0, and 2.6; all $P < .001$). The WOMS score was evaluated at baseline and at 2 years after embolization in 35 knees and showed significant improvement of synovitis vs baseline ($P < .0016$) and no osteonecrosis or other evidence indicating aggressive progression of degenerative changes. There were no major adverse events related to the procedures. Specifically, there was no incidence of tissue necrosis, dermal ulcers, or peripheral paresthesia in any embolized territory during the follow-up period. Moderate subcutaneous hemorrhage at the puncture site in 12 patients resolved within 1 week. Four of seven patients treated with Embozene showed transient cutaneous color change on the treated knee, which resolved spontaneously within 1 month.

A recent study by Bagla et al, showed improvement in the pain scores in 20 patients with knee osteoarthritis. The mean VAS improved from 76 mm \pm 14 at baseline to 29 mm \pm 27 at 6-month follow-up ($P < .01$). The mean WOMAC score improved from 61 \pm 12 at baseline to 29 \pm 27 at 6-month follow-up ($P < .01$). Self-limiting skin discoloration occurred in 65% patients and 10% of patients developed transient plantar sensory paresthesia.

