8.7 Safety Oversight

It is the responsibility of the Principal Investigator to oversee the safety of the study. This safety monitoring will include careful assessment and appropriate reporting of adverse events as noted above, as well as the construction and implementation of a site data and safety-monitoring plan. Medical monitoring will include a regular assessment of the number and type of serious adverse events. Data (demographics, eligibility criteria), screening methods, and adverse events will be assessed by the PI who is a fellowship trained interventional radiologist and licensed physician monthly to ensure study safety, compliance, and integrity/accuracy of data in accordance with the data safety monitoring plan.

Administration of study procedure will be halted when three moderate or higher grade AEs determined to be “related” are reported to the sponsor (PI). The PI will notify the study investigators immediately when the third grade 3 event is reported and enrollment screens will stop accepting new study participants. The study sponsor will convene a meeting with study investigators by teleconference or in writing as soon as possible and will provide recommendations for proceeding with the study. The study sponsor will inform the IRB and FDA of the temporary halt and the disposition of the study.

The outcomes of these reviews, when adverse events are captured will be communicated directly with the IRB. A summary of these reviews will be submitted to the IRB as part of an annual progress report at Continuing Review.

Specific data safety monitoring plan is listed below:

- 1- Vascular injury / non-target embolization to lower extremity, bleeding, access site complications will be monitored as follows:
 - a. On the day of procedure, interventional radiologist (investigator) performing the procedure will assess access site and lower extremity pulses and document
 - b. Day 1 visit / telemedicine visit: investigator will assess for symptoms in the target lower extremity (pain, swelling at access site and document findings
 - c. 4 weeks follow up visit: investigator will assess groin access site for hematoma, pseudoaneurysm and assess lower extremity pulses
- Skin ulceration, cutaneous purpura, plantar or peripheral sensory paresthesia will be monitored as follows:
 - Each follow up visit, an investigator will assess for symptoms and signs in the target lower extremity and document

CONFIDENTIAL

9 Clinical Monitoring/Quality Assurance

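### Visit 4 (day 1) may be a voice call, yet the plan assigns it an examination, a check for skin signs and a pain-score trigger with no scheduled score, so short-lived adverse events may be under-counted

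*Combined protocol and SAP*

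**What the plan says.** Four places govern Visit 4.

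- **Schedule of Activities, table.** The row "Physical exam" is marked at Visit 4, as is the adverse-event row. Pain VAS and KOOS are marked at baseline and at Visits 5 to 8, and are blank at Visit 4.
- **Schedule of Activities, Visit 4 footnote.** The contact may be a "phone call, telemedicine, or in-person IR clinic visit determined by subject's preference and need for physical examination", within plus 3 days.
- **Section 7.3.4.1.** The heading gives day 1 plus or minus 3 days. The text reads "Subjects will be seen in clinic or contacted by phone or per the subject's preference the day following GAE (+3 days". Further assessment and management follow "If AE is suspected based on change in pain scores or functionality". Unlike the later visits, this one has no itemized list of procedures.
- **Section 8.7.** For vascular and access-site problems: "Day 1 visit / telemedicine visit: investigator will assess for symptoms in the target lower extremity (pain, swelling at access site and document findings". For ulceration, purpura and paresthesia: "Each follow up visit, an investigator will assess for symptoms and signs in the target lower extremity and document".

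On what to expect, Section 2.2.2 reports that four of seven patients given this device in a 72-patient study "showed transient cutaneous color change on the treated knee, which resolved spontaneously within 1 month". It also reports puncture-site hemorrhage in 12 of those 72 patients, resolved within a week, and self-limiting skin discoloration in 65% of a separate 20-patient study. Section 10.4.4 defines the safety endpoint as the proportion of patients with each type of adverse event, or with any.

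**The concern.** Section 7.3.4.1 gives detection of early adverse events as the purpose of Visit 4, on the ground that most complications will show by then. If the contact is by voice, the scheduled exam and the Section 8.7 check for signs cannot be carried out. The stated ground for suspicion refers partly to a score that nobody is scheduled to collect that day. Skin discoloration or a groin bruise also need not change pain or function.

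The events that the cited studies lead one to expect are early and short. If they are looked for directly in some patients and left to report and recall in others, the recorded proportion depends partly on how the patient was contacted. In a pilot meant to evaluate safety and feasibility, that proportion is one of the main things the study will be cited for.

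**Working it through.** The plan states no figure on this point, so there is none to reproduce. The check is mainly a comparison of passages.

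**1. Visit mode against task**

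| Task at Visit 4 | Source | Possible by voice call? |
|---|---|---|
| Physical exam | Schedule of Activities | No |
| Skin and sensory signs | Section 8.7 | No |
| Skin and sensory symptoms | Section 8.7 | Yes, if asked |
| Access-site pain and swelling, as symptoms | Section 8.7, day-1 item (names a visit or telemedicine, not a phone call) | Yes, if asked |
| Change in pain score | Section 7.3.4.1 | No score is scheduled in any mode |
| Change in functionality | Section 7.3.4.1 | By asking; no instrument is scheduled |

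**2. Window.** The procedure is day 0. Read literally, the heading allows contact from day 1 − 3 = day −2, before the procedure. The text and footnote allow day 1 to day 1 + 3 = day 4.

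**3. Time to the next scheduled exam.** Visit 5 is day 30 ± 10, so day 20 to 40. From a Visit 4 call on day 1 to 4, the gap is 20 − 4 = 16 days at the shortest and 40 − 1 = 39 days at the longest. A hemorrhage that resolves within 7 days will be gone by then. A color change that resolves within a month may be.

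**4. How the loss would behave (illustration only).** Let p be the true proportion with an event, r the share of Visit 4 contacts made by voice call, and s the chance that a voice call together with later report and recall captures the event. Assume that the other modes capture all events. Then

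recorded proportion = p × [(1 − r) + r × s].

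The documents give neither r nor s. Taking p from the cited studies (0.65 for discoloration; 12/72 = 0.167 for puncture-site hemorrhage) and the 40 patients whose data are required:

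| True proportion (patients) | r | s = 0.5 | s = 0.8 | s = 1 |
|---|---|---|---|---|
| 65% (26.0) | 0.5 | 48.8% (19.5) | 58.5% (23.4) | 65% (26.0) |
| 65% (26.0) | 1 | 32.5% (13.0) | 52.0% (20.8) | 65% (26.0) |
| 16.7% (6.7) | 0.5 | 12.5% (5.0) | 15.0% (6.0) | 16.7% (6.7) |
| 16.7% (6.7) | 1 | 8.3% (3.3) | 13.3% (5.3) | 16.7% (6.7) |

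For example, 0.65 × [0.5 + 0.5 × 0.8] = 0.65 × 0.9 = 0.585. The result ranges from no loss to half of the events, and turns entirely on two unknowns.

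**The case against.** The strongest reply is that an event does not have to be seen to be counted. Section 8.1.1 defines adverse events to include symptoms. The sections on later visits count what the patient reports as well as what the investigator observes. Section 8.3 has the investigator ask at each visit about events since the last one, and already collects onset and resolution times. Section 7.3.3 gives patients a 24-hour physician line. Patients can see their own knee, and paresthesia is something they feel.

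For the access site, the day-1 task in Section 8.7 is worded as symptoms. The site and pulses are examined on day 0 and at 4 weeks, and Section 6.2 adds 2 to 6 hours of monitoring after the procedure. The footnote lets need for examination lead to a clinic visit, and Section 7.3.4.1 does not say that its trigger is the only one.

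All of this stands, and it rules out two stronger readings. A reader might infer that early events are counted by visit mode rather than by occurrence. The documents do not support that, because prompted inquiry and patient report operate in every mode. A reader might also take the share of events no longer visible at Visit 5 as the share lost. That needs an assumed distribution of clearing times, and it measures what can still be seen, not what goes unrecorded.

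What remains is narrower. None of these safeguards delivers the signs assessment that Section 8.7 requires. A patient with no complaint after a voice call may be examined by nobody between day 0 and day 20 to 40.

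**Conclusion.** The point holds as an inconsistency that should be fixed. The plan assigns Visit 4 an exam and a signs check that one of its permitted modes cannot deliver, ties suspicion of an adverse event partly to a score not scheduled there, and gives two windows. The consequence for the data is a risk, not a demonstrated bias: ascertainment of transient, sign-based events may vary with visit mode, and the adverse event rate may be under-counted.

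No size can be given without the voice-call share and the capture rate. Applying the cited rates here is itself an assumption, since Section 2.2.2 gives no particle size for either source and does not name the embolic in the 20-patient study. With a single arm, the effect is on the absolute rate, not on a comparison between arms. Adverse event rates are secondary endpoints, and the events concerned were self-limiting in the cited studies.

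**What to change.** **Reconcile the documents.** Align the Schedule of Activities, its Visit 4 footnote, Section 7.3.4.1 and Section 8.7 on three matters: which assessments apply in each visit mode, what the window is, and what data stand behind the trigger for further assessment. Which clinical rule to adopt is for the investigators. If a day-1 pain score is added, the plan should also say whether the 24-hour withholding of pain medication applies to that contact.

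**Standardize ascertainment.** Use one fixed, prompted checklist of the Section 8.7 events at Visits 4 and 5, asked in the same way in every mode. Where Section 8.7 signs are to be assessed, use an in-person contact or video, which the footnote already allows as telemedicine. Record the Visit 4 mode.

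**Report.** Give early adverse event rates by Visit 4 mode, including patients already treated where the mode was documented, as description only. The footnote steers patients who need an exam to clinic, so a difference between modes would be confounded and would not by itself show under-counting.

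The cost is some rewording, a one-page checklist and one data field; no visit is added. Some patients who would have preferred a voice call would need a video link.
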